Physical Activity. We will use two measures of PA. **Accelerometers:** Participants will be instructed to wear accelerometers over seven consecutive days. The Actigraph GT3X 16Mb activity monitor is small, light weight, and designed to detect vertical acceleration that allows for the detection of normal human motion and reject high frequency vibrations encountered in activities such as operation of a lawn mower. The filtered acceleration signal is digitized and the magnitude is summed over a user-specified time interval. At the end of each interval, the summed value or activity "count" is stored in memory and the integrator is reset. For the proposed study, participant will wear the monitor for one week and a 1-minute time interval will be used. Freedson et al.^{82, 83} assessed the validity and inter-instrument reliability of the ActiGraph monitor in adults. Activity counts were strongly correlated with energy expenditure during treadmill walking and running ($r = 0.86$) We will determine the total time per day spent in moderate and vigorous PA by using adapted cut points previously established by Freedson et al.^{82, 83} Participants will need to wear the accelerometer for at least 10 hours per day and on at least 3 of the 7 days for reliable measurement of activity. [name] and [name] have used activity monitors in previous studies and had high compliance (81%) with the activity monitor protocol in the pilot study⁸⁴. (See Appendix D for accelerometer log). **Self Report:** We will use a comprehensive self-report measure to characterize participants' type, pattern, nature, and amount of PA in a typical week. The Community Health Activities Model Program for Seniors Physical Activity Questionnaire (CHAMPS) is a 41-item self-report measure of PA was developed originally for older adults, but it has been used with general adult populations^{64, 85}. We will use the measure as originally developed, but we will modify those items that are geared for older adults to be age-neutral (e.g., replace "visit a senior center" with "visit a community center"). For the proposed study, we will use total minutes per week spent in moderate and vigorous PA as the primary outcome measure. The CHAMPS has strong psychometric properties and has also been shown to be sensitive to change in intervention studies⁸⁵.

Secondary Outcome Measures:

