Primary Outcomes (Aim 1 & Aim 2b). MVPA outcomes will be self-reported behavior of a typical week measured with the CHAMPS instrument (minutes/week MVPA) and objective measurement from the accelerometer (minutes/day MVPA). Averages for each MVPA outcome at each time-point will be calculated and compared for the intervention versus the attention-control group and ANOVA tests will be performed to evaluate for significant differences between groups. Assessment will be made to determine direction- e.g. increases or decreases- of change between baseline and post-intervention, and baseline and 6-month follow-up. Using STATA 11 to conduct our modeling we will use a regression that is both multilevel and temporal in nature. Mixed-effects regression can be conducted using the `xreg`, `xtgee` and `xtlogit` command in STATA 11 SE¹⁰², depending on the structure of the outcome variable. In this case, time-points of measurement are nested within subjects in a random intercept model. Random coefficient modeling will be conducted using random effects variables at level 2 (subject level) that will be both fixed (nativity, occupation, education, baseline age, etc.) and time varying (perceptions over time, behavior over time, income). Below we represent the equation for a binomial outcome model

$$\log(\mu_{ij}) = x'_{ij} \beta_1 + x'_{ij} \beta_2 \quad (i = \text{level 1-repeated MVPA measures over time}, j = \text{level 2- Individual level covariates})$$

Whereas β_{ij} represents the expected change in the log of the mean unit change of x_{ij} A one unit change in x_{ij} corresponds to an increase β_{ij} in the log of the average.

Secondary Outcomes (Aim 2a). Similar methodology will be implemented in this analysis as in AIM 1. Our outcome variables

FORM C

IRB #	HSC20110460H
-------	--------------

for aspect of the study will be physical fitness, BMI and anthropometric measures of body fat. Averages for physical fitness, BMI and body fat will be calculated for intervention versus the attention-control group and ANOVA tests will be conducted to evaluate significant cross-sectional differences between the intervention and attention-control groups. Evaluation of temporal changes between each time-point will be made. Mixed effect regression models will be conducted as described in Aim 1.

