Mediation Analyses (Aim 2c). As outlined by MacKinnon^{103, 104}, mediation will be assessed by conducting two regression models. The first model will regress change in the hypothesized mediator (e.g., social support, self-efficacy) on intervention group (intervention vs. control) (α coefficient path). The second model will regress change in the outcome variable (e.g., MVPA) on intervention group and change in the hypothesized mediator (β coefficient path). To assess the magnitude of the effect for each potential mediator, the Sobel-Goodman test will be conducted using *sgmediation* in STATA 11 SE¹⁰⁵. This method provides direct and indirect effect estimates, proportion of effect explained by mediator, and significance testing.

Attrition Analyses. We will compare all baseline demographic, cognitive, and behavioral variables of participants lost to follow-up with baseline data of the cohort, to determine possible selective or differential (by treatment condition) attrition. For instance, analyses will be conducted to determine if participants with greater weight or lower PA disproportionately drop out of the study. Selective attrition (i.e., do dropouts differ from the cohort as a whole?) will be considered a threat to external validity or generalization. Presence of differential attrition (i.e., difference in dropouts between treatment conditions) will be considered a threat to internal validity. To the extent that some subjects are lost to follow-up, analysis for the primary and secondary hypotheses will be carried out under the intent-to-treat principle.

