Qualitative Data Analysis Plan. Audio recordings of interviews will be transcribed verbatim in the source language and returned to the PI in paper and electronic (Microsoft Word) formats. A data collection assistant will review the paper transcripts for quality control purposes to make sure that the paper and electronic transcripts are as accurate and reflective of the interview as possible. All identifying information will be removed from transcripts. The transcript files will be imported into AtlasTi software for qualitative data management and analysis. All data in paper format will be stored in locked cabinets in locked offices. [name] will lead the qualitative analysis of the interview data in the source language, using thematic analysis procedures and the constant comparison method^{97,106}. For presentation and dissemination, selected excerpts of the Spanish-language qualitative data will be translated into English.

Power and Sample Size: Power calculations were conducted to determine the minimum detectable effect size based on a desired power achievement =0.80 using Optimal Design¹⁰¹. Setting the standard effect size to 0.50 and an expected intraclass correlation of .01, we have calculated a minimum number of 83 subjects per site will be needed. Based on a 76% retention rate from the pilot study, we will sample an additional 25 subjects to maintain statistical power throughout study duration for a total of 108 per site and an overall total of 864 subjects.

In-Depth Interviews: With a resulting sample of 96 interviews, we anticipate meeting the requisites of saturation and sufficiency⁹⁶. Saturation refers to the point in the study at which analysis of the interview data results in no new properties or dimensions⁹⁷. The greater the amount of pertinent (on-topic) data obtained from participants, the smaller number of participants required for saturation; thus, well-devised and conducted interviews with skilled probing reduces the need for large sample sizes in order to fully assess the phenomena under study⁹⁸. Sufficiency is the extent to which the participant sample encompasses the range of variability in the participant characteristics, especially those of known relevance to the topic⁹⁹. Due to the relative homogeneity of our participants, a sample of 96 interviews is expected to be sufficient.

6.b. List of the study intervention(s) being tested or evaluated under this protocol

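### The protocol promises intent-to-treat for women lost to follow-up, but the only between-arm test it states is a completers' ANOVA, and the mixed model that could keep the promise is not made primary

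*Protocol*

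**What the plan says.** All of the following stands in Protocol section 6.a.

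- **Attrition Analyses.** Baseline data of women lost to follow-up are compared with those of the cohort. Differential loss by arm is called a threat to internal validity. The paragraph closes: "To the extent that some subjects are lost to follow-up, analysis for the primary and secondary hypotheses will be carried out under the intent-to-treat principle".
- **Primary Outcomes (Aim 1 & Aim 2b).** The between-arm test is introduced thus: "Averages for each MVPA outcome at each time-point will be calculated and compared for the intervention versus the attention-control group and ANOVA tests will be" (the sentence goes on to give its aim, which is to detect differences between the arms). The secondary-outcomes paragraph repeats this approach. The primary-outcomes paragraph then describes a mixed-effects regression with time-points nested within women and a random intercept, and lists `xtgee` among the possible commands. Its equation is given for a binomial outcome. Neither the equation nor the listed covariates include arm or arm-by-time.
- **Physical Activity measures.** "Participants will need to wear the accelerometer for at least 10 hours per day and on at least 3 of the 7 days". The pilot "had high compliance (81%) with the activity monitor protocol in the pilot study". CHAMPS self-report gives a second MVPA measure that needs no wear time.
- **Power and Sample Size.** "Based on a 76% retention rate from the pilot study", the target of 83 per site is raised by 25 to 108, or 864 women in all.

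**The concern.** Intent-to-treat says which arm a woman is analysed in. It does not say what to do when her outcome is absent. An average at 16 or 40 weeks contains only women who gave a value at that visit, so the stated test compares completers, and the protocol would present that result as intent-to-treat.

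The attrition section diagnoses selective or differential loss but does not correct for it. The arms make different demands: weekly sessions with group exercise in one, twice-monthly safety sessions in the other. Loss related to initial activity could therefore differ by arm. If less active women left the PA arm more readily, the completers' contrast would favour the intervention with no true effect.

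**Working it through.** **1. Inputs from the protocol.** Retention 76% (pilot); monitor compliance 81% (pilot, denominator and visit not given); 83 women needed per site; 108 enrolled per site; 8 CRCs, 4 per arm; effect 0.50 SD; ICC 0.01.

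**2. The plan's own inflation step.** 83 / 0.76 = 109.2, so 110 against the stated 108. In reverse, 108 × 0.76 = 82.1 against 83. The step reproduces within 2%, so the protocol itself plans on about 24% loss.

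**3. Women without a value.**
- Lost to follow-up: 0.24 × 864 = 207.
- No valid accelerometer week, if the 81% applies among retained women: 1 − 0.76 × 0.81 = 0.384, and 0.384 × 864 = 332. About 66 per site remain (108 × 0.6156 = 66.5).
- If the 81% already counts dropouts, the accelerometer figure stays near 24%.

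**4. Power is not the issue.** With a noncentral t on 8 − 2 = 6 df and two-sided alpha 0.05 (assumed; the protocol gives none), power at 0.50 SD and ICC 0.01 is 0.976 with 83 per site and 0.958 with 66.

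**5. Bias of the completers' contrast.** The assumptions here are not in the protocol: no true effect; retention in the PA arm rises with baseline MVPA (Z, in SD units) by a logistic curve with odds ratio 1.5 to 2.0 per SD; loss in the control arm is random at the same overall rate; the baseline to follow-up correlation r is 0.4 to 0.6. Then bias = r × E[Z | retained].

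| Loss | Odds ratio | E[Z given retained] | Bias, r = 0.4 | Bias, r = 0.6 |
|---|---|---|---|---|
| 24% | 1.5 | 0.0945 | 0.038 | 0.057 |
| 24% | 2.0 | 0.1534 | 0.061 | 0.092 |
| 38% | 1.5 | 0.1502 | 0.060 | 0.090 |
| 38% | 2.0 | 0.2413 | 0.097 | 0.145 |

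The range is about 0.04–0.09 SD at 24% loss and 0.06–0.14 SD at 38%. Against the planned 0.50 SD that is 8–18% and 12–29%.

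**6. Against the standard error.** SE = sqrt(2(1 + (m − 1) × 0.01) / (4m)), which is 0.105 for m = 82 and 0.112 for m = 66.5. The bias is 0.36–0.88 and 0.54–1.30 standard errors.

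**7. Which planned analysis removes it.** In a simulation with no true effect (38% missing, odds ratio 2, r = 0.5; 60 replicates), the time-point contrast was biased by 0.11 SD and GEE with independence working correlation also by 0.11 SD. The likelihood model with baseline in the response gave about −0.02 SD, within simulation noise of zero. With stronger selection (log-odds slope 1.0 per SD, r from 0.3 to 0.7), the completers' contrast was biased by 0.07–0.15 SD at 24% and 0.10–0.23 SD at 38%. Adjusting for baseline left 0.00–0.01 SD.

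**The case against.** The strongest reply is that the remedy is already planned. A random-intercept model of repeated MVPA keeps women who have only a baseline value. Fitted by likelihood with arm-by-time terms, it is valid when loss depends on observed values. A reader might infer that the plan leaves attrition bias wholly uncorrected; the protocol does not support that. What stands is narrower: the model is not named primary, no arm contrast is written, and one permitted command need not give this protection.

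A reader might also infer that over a third of women will have no follow-up MVPA at all. That does not follow. The 38% concerns the accelerometer only and multiplies two pilot rates with unstated denominators. Retained women can still give CHAMPS minutes, and part of the payment depends on returning a monitor with sufficient data. Even the 24% has no stated time-point: a woman lost after 16 weeks has a 16-week value.

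Nor does the protocol say that less active women are expected to drop out. It plans to check whether they do.

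Imputation rules and sensitivity analyses are commonly left to a statistical analysis plan, so their absence is not a fault. The mismatch between the intent-to-treat promise and the time-point ANOVA remains, because this document states both.

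Finally, no false-positive rate is claimed for the ANOVA. Such a rate would need a cluster-adjusted reference test, and the protocol states no cluster adjustment for its ANOVA.

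**Conclusion.** The point holds in this limited form. The stated between-arm test is a completers' analysis and does not deliver the promised intent-to-treat analysis; a suitable model is mentioned but not fixed as the test. The protocol's figures put about 24% of women at risk of having no value, and up to 38% for the accelerometer on the multiplication assumption.

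The size of the bias rests entirely on the assumed loss mechanism. It needs selection that differs by arm: if loss depended on baseline equally in both arms, the bias in the contrast would cancel when there is no effect. The calculation also assumes that non-wear depends on baseline activity as dropout does. The likelihood model removes bias from loss explained by observed values, not from loss driven by unobserved follow-up activity. This should be changed, since the correction is nearly free, but it is not evidence that the trial's result would be wrong.

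**What to change.** In section 6.a, under Primary Outcomes and Attrition Analyses:

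1. Name as primary a likelihood-based mixed model fitted to all enrolled women by the arm of their CRC. Put baseline, 16-week and 40-week MVPA in the response, with arm-by-time contrasts and random effects for woman and CRC.
2. State that it assumes missing at random, and let this replace the bare intent-to-treat sentence.
3. Treat monitor weeks that fail the wear rule as missing.
4. Do not use `xtgee` for this test, and keep the time-point ANOVA as descriptive.

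Imputation and sensitivity details can go in the statistical analysis plan. The cost is wording and slightly more programming, with no new data; intervals may be slightly wider.
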